3.0 Background

- 3.1 Point-of-Care Ultrasonography (POCUS) has been recognized as a powerful tool to evaluate critically ill patients. Using gastric ultrasonography, we can evaluate gastric volume and the types of contents as well as gall bladder size. The cross-sectional area of the gastric antrum is used to calculate the gastric volume. The full stomach state in pediatric patients scheduled for elective surgery is low at only 0-1%. However, it is unknown how lack of appropriate NPO time affects gastric volume and contents as well as gall bladder size. The gallbladder stores bile and starts to empty after the presence of fatty food in duodenum. Gallbladder emptying also

requires relaxation of the sphincter of Oddi, which may be disturbed by opioids. Therefore, it may be useful to evaluate patient NPO status. The diameter of great vessels has been used to evaluate patient volume status in pediatric patients.

- 3.2 Point-of-care gastric ultrasound had a sensitivity of 1.0 and a specificity of 0.975 to detect a “full stomach”. ¹ Using point-of-care gastric ultrasound, a previous study reported that 0-1 % of the healthy pediatric patients scheduled for elective surgery were at risk of pulmonary aspiration ^{2 3} However, 35 % of the adult patients scheduled for unplanned surgery had a full stomach even after ≥ 6 hours of NPO time ⁴ The normal gallbladder sizes in healthy children has been evaluated after fasting in previous report. ⁵ There is no article which reports the relationship between NPO state and gallbladder size.
- 3.3 Rapid sequence induction (RSI) is widely used to avoid pulmonary aspiration during anesthetic induction. However, RSI is the risk factor for oxygen desaturation and other airway complications when compared to standard anesthetic induction techniques. The current study will help identify which trauma patients are truly at risk for aspiration and therefore require RSI.

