4.0 Study Endpoints

- 4.1 The primary study endpoint is the number (percentage) of patients in the urgent, emergent group with a full stomach state as assessed by gastric volume and contents despite an appropriate NPO time.
- 4.2 The secondary endpoint will be to determine gall bladder size between fasted patients undergoing elective versus urgent/emergent surgery. The other endpoint will be to evaluate the preoperative volume status.

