6.0 Procedures Involved*

6.1 This is a prospective observational study that will be conducted in 300 patients, ranging in age from 2 to 18 years who are scheduled for routine, urgent or emergent surgeries. There will be no change in clinical practice regarding choice of anesthetic technique as a result of this research study. Before surgery in the pre-operating area, the ultrasonographer will evaluate the gallbladder size and volume. Procedure time will be recorded for the ultrasonography. Demographic data, including age, sex, height, weight, nil per os time, preoperative symptoms, administered opioids, and types of the surgery will be recorded.

6.2

Ultrasound protocol

All ultrasound scans will be performed by study investigators by using Sonosite X-porte (Sonosite Inc. USA) machine and 3-8 MHz curved linear probe with abdominal setting. The investigators have enough experiences of POCUS.

All patients will be lying supine, followed by RLD position. Patients were placed in the supine position, followed by the right-lateral decubitus (RLD) position. In cases where it is not feasible to place the patient in the right lateral decubitus position, the patient can be placed in a 45 degree head up position with a bump placed under the left hip. The gastric antrum is identified in a sagittal plane between the left lobe of the liver and the pancreas at the level of the descending aorta and supra mesenteric artery or inferior vena cava, as previously reported.⁶ One video clip will be recorded for each patient in the supine and RLD positions. The qualitative measurements (empty versus nonempty) will be reported to the attending anesthesiologist. The quantitative measurements will be performed at later time. The quantitative exam is performed using the cross-sectional area of the gastric antrum. The CSA of the antrum will be measured with a free-tracing method to follow the outer margin of the antrum corresponding to the serosa.⁷ The gastric volume will be calculated using the following formula.⁸

$$\text{Gastric volume (ml.kg}^{-1}\text{)} = [-7.8 + 0.035 \times \text{CSA (mm}^2\text{)} + 0.127 \times \text{age (months)}]/\text{body weight (kg)}.$$

The qualitative measurements will be performed using 3-point grading scale.⁹

Grade 0: no fluid visible in the antrum in either the supine or RLD position.

Grade 1: antral fluid visualized only in the RLD position.

Grade 2: antral fluid visualized in both the supine and RLD position.

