“Full stomach is defined by the visualization of solid contents or frost-grass pattern and/or by a calculated gastric fluid volume $>1.5 \text{ ml.kg}^{-1}$.

The gallbladder size and volume will be evaluated as previously reported.⁵

The gallbladder volume was calculated as following formula.

Volume = $0.52 \times L$ (the greatest length) $\times W$ (anterior posterior dimension) $\times W$ (transverse width)

B and C are assumed to be equal.

[figure not shown]

FIGURE 1. Method of sonographic measurement of gallbladders. The gallbladder volume was measured using the prolate ellipsoid volume formula: $V = 0.52 \times L \times W \times W$. A is the greatest length (L), B is the anteroposterior dimension (W) and C is the transverse width (W). B and C were assumed to be equal.

The diameter of great vessels will be measured in supine position.

Demographic data, including age, sex, height, weight, nil per os time, preoperative symptoms, administered opioids, and types of the surgery will be recorded.

6.3 There are no foreseeable risks associated with the use of ultrasound.

6.4

Ultrasound data will be stored in the ultrasound machine. The research team will transmit the data to the password-secured server and store as MP4 file and JPEG file. The data will then be deleted from the ultrasound machine.

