10.0 Inclusion and Exclusion Criteria*

10.1 Potential subjects will be identified by reviewing the surgery schedule in Epic and will be recruited from the main OR pre-operative area the day of their surgery.

10.2 Inclusion criteria: ASA 1-3 patients aged 2-18 years of scheduled for elective, urgent, or emergent surgery under general anesthesia.

Exclusion criteria: History of upper gastro-intestinal surgery.

10.3 We will include children, and will not include adults unable to consent, pregnant woman, and prisoners as they are not part of our usual patient population.

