12.0 Local Number of Subjects

12.1 300 (100 in each group of routine, urgent, and emergent cases).

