17.0 Data Management* and Confidentiality

- 17.1* Summary statistics will be described by using means and standard deviation for parametric variables and median with interquartile ranges (IQRs) for nonparametric variables. The Kolmogorov-Smirnov test will be used to assess the normality of data. Bivariate analysis for paired continuous variables will be conducted using the paired t test and Wilcoxon signed-rank test, and for independent continuous variables it is conducted using the independent samples t-test and Wilcoxon rank-sum test. Bivariate analysis for categorical variables will be conducted using the Chi-square test or Fisher's exact test, where appropriate. P value less than 0.05 is considered to indicate statistical significance. Statistical analysis will be done using SAS 9.4 and G*Power version 3.1.9.2.

Primary Outcome: The primary outcome is the proportion of full stomach state.

- 17.2* Research records will be stored in a locked cabinet and password protected computer. Only certified research personnel will be given access to identifiable subject information
- 17.3* Following publication of study results, research records will be stored for a period of 3-5 years and then will be destroyed by placing in a secure shredding bin.

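### Volume status rests on great-vessel diameter in children aged 2 to 18, with no size-standardised measure and no size-adjusted comparison planned

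*Combined protocol and SAP*

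**What the plan says.** - **Purpose.** Background 3.1 gives the reason for the measurement: "The diameter of great vessels has been used to evaluate patient volume status in pediatric patients".
- **Endpoint.** Section 4.2, after the primary and the gallbladder endpoints, adds: "The other endpoint will be to evaluate the preoperative volume status". It names no variable, cut-off or group comparison.
- **Measurement.** Section 6.2 says "The diameter of great vessels will be measured in supine position". Neither it nor section 5.0 names the vessel or mentions an index to height, weight or body surface area (BSA), a z-score, or a ratio between vessels.
- **Population.** Section 6.1 plans the study "in 300 patients, ranging in age from 2 to 18 years", and 10.2 sets the same age range. Section 12.1 gives three urgency groups of 100. They are not randomised, and no matching or stratification on age is described.
- **Analysis.** Section 17.1 states "for independent continuous variables it is conducted using the independent samples t-test and Wilcoxon rank-sum test", and "P value less than 0.05 is considered to indicate statistical significance". No regression, analysis of covariance or other adjusted method appears in the documents. Section 17.1 does not mention vessel diameter.
- **Data available.** Sections 6.1 and 6.2 record age, sex, height and weight. The gastric volume formula in 6.2 uses age and divides by body weight; vessel diameter has no counterpart to this.

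**The concern.** A vessel widens as a child grows, so across ages 2 to 18 a diameter carries information about body size as well as filling. The plan allows for size in the gastric measurement but not here. If the generic tests in 17.1 are applied to diameter, two things follow.

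1. **Lost power.** Even when the groups have the same age mix, growth-related spread enters the error term and can hide a real difference in volume status.
2. **Possible bias.** If one urgency group is older or larger on average, its vessels will be wider for that reason alone. Depending on direction, this can look like a difference in volume status or cancel one. The rank-sum test is affected in the same way as the t-test.

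What is at stake is whether this endpoint can be interpreted, not the main result of the study.

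**Working it through.** **No stated figure to reproduce.** The documents give no mean, SD, effect size or power for vessel diameter. What follows is a range under stated assumptions.

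**Inputs from the documents:** 100 per group (12.1); ages 2-18 (6.1, 10.2); significance level 0.05 (17.1), taken as two-sided because this is not stated.

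**Assumptions, not in the documents:** ages uniform from 2 to 18; mean height rising linearly from 85 cm at age 2 to 170 cm at age 16, then flat; diameter proportional to height; residual coefficient of variation (CV) of diameter given height between 10% and 30%.

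**Step 1: share of variance due to size.** The assumed heights have mean 132.8 cm and SD 26.9 cm, so the CV of height is 26.9/132.8 = 0.203. With residual CV c:

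- raw CV = √[0.203² + c²(1 + 0.203²)]
- share due to size = 0.203² / (raw CV)²

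For c = 0.20, raw CV = √(0.0411 + 0.0416) = 0.288 and the share is 0.0411/0.0827 = 50%.

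**Step 2: power, groups balanced on size.** For a true relative difference δ, power ≈ Φ(δ/[s√(2/100)] − 1.96), where s is the raw CV for the unadjusted test and c for the adjusted one. For δ = 10% and c = 0.20:

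- unadjusted: 0.10/(0.288 × 0.1414) = 2.46, power 69%
- adjusted: 0.10/(0.20 × 0.1414) = 3.54, power 94%

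Using c itself takes the residual SD at mean height. Averaged over the assumed heights it is larger by √(1 + 0.203²) = 1.02, so the adjusted figures are slightly favourable.

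**Step 3: false positives with no true volume difference.** Under the height assumption, one year of mean age moves mean diameter by about 4.4%, and two years by about 8.8%. The rejection rate is Φ(k − 1.96) + Φ(−k − 1.96), with k = shift/(raw CV × 0.1414). For c = 0.20 and one year, k = 0.044/0.0407 ≈ 1.08, giving 19%.

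| Residual CV | Raw CV | Share due to size | Power, 5% difference: raw / adjusted | Power, 10% difference: raw / adjusted | False positives, 1-year gap | False positives, 2-year gap |
|---|---|---|---|---|---|---|
| 10% | 22.7% | 80% | 34% / 94% | 88% / >99% | 28% | 78% |
| 15% | 25.4% | 64% | 29% / 65% | 80% / >99% | 23% | 68% |
| 20% | 28.8% | 50% | 23% / 42% | 69% / 94% | 19% | 58% |
| 25% | 32.6% | 39% | 19% / 29% | 58% / 81% | 16% | 48% |
| 30% | 36.7% | 30% | 16% / 22% | 49% / 65% | 14% | 39% |

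**Step 4: a second scaling as a check.** Assume instead that diameter follows the square root of BSA, with BSA = √(height in cm × weight in kg / 3600) and illustrative body sizes.

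- Age 2 (86 cm, 12 kg): BSA 0.54 m². Age 18 (172 cm, 68 kg): BSA 1.80 m². Diameter ratio √(1.80/0.54) ≈ 1.8.
- Age 7 (122 cm, 23 kg): BSA 0.88 m². Age 9 (133 cm, 29 kg): BSA 1.04 m². Diameter ratio about 1.08, a shift of about 8%.

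The two scalings agree that a 2-year gap in mean age is worth about 8-9% of diameter.

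**The case against.** The strongest reply is that the plan never says it will test unscaled diameter between groups. Section 4.2 states a contrast for gallbladder size but none for volume status, and 17.1 is a generic list that does not name vessels. Section 6.2 speaks of vessels in the plural, which would be compatible with a ratio. This stands: the unadjusted test of diameter is the default reading of a plan that is silent, not a stated choice. But no alternative is given either, so nothing in the plan prevents that analysis.

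A reader might also infer that body size dominates the comparison. The documents do not support this. They contain no variance figures, and under the assumptions above size accounts for half or more of the variance only when the residual CV is about 20% or less.

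A reader might further infer that the comparison is bound to be biased. That needs a difference in age or size between the groups. Without randomisation or matching it is plausible, but the documents neither report nor predict it. With similar groups the cost is lost power only.

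Finally, the endpoint ranks low. It is absent from the objectives and hypothesis in section 2.0, and the full-stomach proportion, which is the primary outcome, does not depend on it. This limits the importance of the point but does not remove it.

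**Conclusion.** The concern holds in a conditional form. The plan provides neither a size-standardised vessel measure nor an adjusted comparison, over an age range in which body size varies greatly. If the listed two-sample tests are applied to diameter:

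- power for a true 10% difference is 49-88%, against 65% to over 99% with adjustment for size;
- with no true difference, a 1-year gap in mean age raises the false-positive rate from 5% to 14-28%, and a 2-year gap to 39-78%.

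These ranges rest on the assumed growth curve, proportional scaling and residual CV of 10-30%, and the age gaps are illustrative. The direction of the power loss is the same in every scenario examined; its size is uncertain. The change is worth making because a better analysis is available from data already collected, but it concerns a lower-ranked endpoint and leaves the primary endpoint untouched.

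**What to change.** - **Section 6.2:** name the vessel or vessels whose diameter is measured.
- **Section 17.1:** state that diameter will be compared between the urgency groups with a linear model that includes group, body size and age, in place of an unadjusted test of diameter. Enter body size on a scale suited to a linear dimension, such as height or the square root of BSA calculated from recorded height and weight.
- **Section 4.2:** state which groups are compared for volume status.

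The cost is wording only, because age, height and weight are already recorded.

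A vena cava to aorta diameter ratio could be added as an option, but only if both vessels are measured in the supine scan. Section 6.2 lists the inferior vena cava as an alternative landmark for the antral view, so it cannot be assumed that both vessels are captured. Requiring both could change image acquisition as well as the analysis text.

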7.0 Data and Specimen Banking*

N/A

8.0 Sharing of Results with Subjects*

8.1 Results will not be shared with subjects.

9.0 Study Timelines*

An individual study subject's participation in the study should last approximately 10 minutes total.

All study subjects should be enrolled within 1 year of study start.

The study should be completed within 18 months of study start.

10.0 Inclusion and Exclusion Criteria*

10.1 Potential subjects will be identified by reviewing the surgery schedule in Epic and will be recruited from the main OR pre-operative area the day of their surgery.

10.2 Inclusion criteria: ASA 1-3 patients aged 2-18 years of scheduled for elective, urgent, or emergent surgery under general anesthesia.

Exclusion criteria: History of upper gastro-intestinal surgery.

10.3 We will include children, and will not include adults unable to consent, pregnant woman, and prisoners as they are not part of our usual patient population.

11.0 Vulnerable Populations*

11.1 This study presents no more than minimal risk as it only involves ultrasound which is non-invasive, and written consent is normally not required.

12.0 Local Number of Subjects

12.1 300 (100 in each group of routine, urgent, and emergent cases).

13.0 Recruitment Methods

13.1 Potential subjects will be recruited in surgical preoperative area on the day of the surgery. The research team will contact the guardian/parents and obtain verbal consent. Verbal assent will also be obtained from age appropriate patients.

13.2 The patients to be recruited are those who are scheduled for surgery under general anesthesia in NCH operating rooms.

13.3 Using Epic, the research team will check the patients scheduled for unplanned surgery in the NCH operating rooms.

14.0 Withdrawal of Subjects*

N/A

15.0 Risks to Subjects*

- 15.1* Although not likely, there may be a potential risk for breach of patient health information. There is no study related physical risk to study subjects associated with this study. All study related procedures are non-invasive.
- 15.2* Subject information will not be given to any other investigators. Subjects and their information will be closely monitored and guarded by study staff; there will be limited access to patients and their information by trained study staff; and subject information will only be shared and discussed between study staff specific to this study. Subject PHI will be stored in a locked cabinet, and will be stored and maintained in password protected computer files.

16.0 Potential Benefits to Subjects*

- 16.1* The qualitative finding will be given to the attending anesthesiologists. This information may impact subsequent anesthetic induction.

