1.0 Study Summary

Study Title	Ultrasonographic evaluation of gastric volume and contents before surgery in children
Study Design	Prospective, non-blinded observational study
Primary Objective	The primary objective of this study is to evaluate gastric volume and contents in patients who are scheduled for elective, urgent, and emergent surgery
Secondary Objective(s)	None
Research Intervention(s)/ Investigational Agent(s)	There will be no change in anesthetic management or use of investigational agents.
IND/IDE #	Not applicable
Study Population	Patients who are scheduled for elective, urgent or emergent surgery
Sample Size	300 (100 in each group)
Study Duration for individual participants	Less than 10 minutes
Study Specific Abbreviations/ Definitions	CSA=cross sectional area POCUS=Point-of-Care Ultrasound RSI=Rapid Sequence Induction RLD=right lateral decubitus

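### Does reporting the unmasked bedside ultrasound read to the attending anesthesiologist bias the primary full-stomach endpoint?

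*Combined protocol and SAP*

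**What the plan says.** Section 1.0 labels the study "Prospective, non-blinded observational study". Section 6.2 states "All ultrasound scans will be performed by study investigators" and then separates two kinds of measurement. For the first, "The qualitative measurements (empty versus nonempty) will be reported to the attending anesthesiologist". For the second, "The quantitative measurements will be performed at later time". The same section grades the antrum 0 to 2 according to whether fluid is seen in neither position, in the right lateral position only, or in both.

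Section 4.1 sets the primary endpoint as the percentage of urgent and emergent patients "with a full stomach state as assessed by gastric volume and contents despite an appropriate NPO time". The definition at the end of section 6.2 can be met in two ways, joined by and/or: "visualization of solid contents or frost-grass pattern", or a calculated volume above 1.5 ml/kg. Clips are recorded in both positions, and section 6.4 has the team "store as MP4 file and JPEG file".

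On the consequence for care, section 16.1 says of the qualitative finding: "This information may impact subsequent anesthetic induction". Section 6.1 says the research will not alter the choice of anesthetic technique, and sections 1.0 and 5.0 say much the same in looser terms.

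**The concern.** Only the quantitative measurement is deferred, so at first reading the bedside look seems to do double duty, informing the attending and also settling the contents part of the primary endpoint. The operator is an investigator, no masking is described, and section 2.2 states a directional hypothesis of larger gastric volume with stress, pain and opioids. Someone who knows the case is an emergency, and that the call may influence induction, might call an unclear antrum full more readily than in an elective child. Because either route suffices, a call of solids makes the patient full whatever volume is calculated later. The unplanned proportion would then be too high, and a comparison with elective patients could show a difference that is not real.

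The wording adds to the unease. A study said to leave anesthetic technique unchanged also says its finding may affect induction.

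**Working it through.** **Does the disclosed read feed the endpoint?** The three descriptions side by side:

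| Read | Categories | When | Yields the solids call? |
|---|---|---|---|
| Reported to the attending (6.2) | empty / nonempty | before surgery | No: nonempty includes clear fluid |
| Grade (6.2) | 0, 1, 2, by visible fluid | not stated | No: fluid only |
| Endpoint contents route (end of 6.2) | solids or frost-grass appearance | not stated | This is the call itself |

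A nonempty or Grade 2 antrum holding clear fluid is full only if the volume exceeds 1.5 ml/kg. Neither described read therefore determines the endpoint. The text leaves the reader and timing of the solids call undefined, and the stored clips allow it to be made later.

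**Can disclosure change the outcome?** The scan precedes induction, so a changed induction cannot alter what was in the stomach. What remains is a reader who may know the surgical group, and that would be so without any report to the attending.

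**How large could a lean be?** The documents give no figure for it, so the specificity losses below are assumptions. From section 3.2: sensitivity 1.0 and specificity 0.975 (for full stomach overall, not contents alone), an elective rate of 0–1%, and an adult unplanned rate of 35%.

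Observed rate = p × 1.0 + (1 − p) × (1 − specificity).

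- p = 0.01: 0.01 + 0.99 × 0.025 = 3.475%; at specificity 0.965, 0.01 + 0.99 × 0.035 = 4.465%. The shift is 0.99 points, or 0.0099 × 200 = 1.98 patients in 200.
- p = 0.35: 0.35 + 0.65 × 0.025 = 36.625%; at 0.965, 0.35 + 0.65 × 0.035 = 37.275%. The shift is 0.65 points, or 0.0065 × 200 = 1.30 patients in 200.

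Chance of a false result with unplanned higher, by exact binomial enumeration with a two-sided Fisher test at 0.05. The true rate is 1% everywhere, with 100 elective against 200 unplanned patients and elective specificity kept at 0.975:

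| Loss of specificity, unplanned groups | Observed unplanned rate | False result |
|---|---|---|
| 0 points | 3.475% | 1.0% |
| 1 point | 4.465% | 3.1% |
| 2 points | 5.455% | 7.1% |
| 2.5 points | 5.95% | 9.9% |
| 5 points | 8.425% | 31.7% |

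With 100 against 100, counting rejections in either direction, Fisher's test gives 1.4%, 6.6% and 21.8% at losses of 0, 2.5 and 5 points.

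Tipping point: with 3/100 elective patients full, 20/200 unplanned gives p = 0.037 and 19/200 gives p = 0.058. With equal true rates of 1%, 20/200 implies a specificity of 1 − (0.10 − 0.01)/0.99 = 0.909, which is 6.6 points below 0.975.

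At true rates of 1% and 35%, 100 per group gives power above 99.9%. A lean of this size would not change the conclusion there.

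These calculations leave out the restriction to patients with appropriate NPO time, because the plan does not say how many there will be.

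**The case for a change.** The strongest reply is that declaring a study non-blinded does not control the bias. The contents call is subjective, it is sufficient on its own, and the expected direction is stated in advance. The 35% is an adult figure and the documents give no pediatric unplanned rate; if that rate is low, a lean of a few points matters. Rereading stored clips without knowledge of the group would need no extra patients or scans.

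Part of this stands. Bias in the reading is possible, and the solids call is not assigned to anyone. But three things weaken the case for a change.

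- The error rates need both an assumed loss and a true rate of 1% in every group. They also use a pooled 100 against 200 comparison that the plan does not specify: section 4.1 defines a percentage within the unplanned patients, and section 17.1 lists tests for categorical variables without naming a primary contrast.
- A masked reread of contents alone would leave the free-traced antral area unmasked, and volume alone also makes a patient full. The safeguard would be partial, at the cost of another reader for 300 patients' clips.
- Schedule screening in section 13.3 is done by the research team, and section 25.1 has coordinators and associates enrolling. This does not show that the person scanning selects the cases, although that person may still know the group.

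The conflict between sections 6.1 and 16.1 is real as written.

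**Conclusion.** No change to the plan follows. The documents do not show that the result given to the attending sets the primary endpoint, and its categories could not do so. What is missing is operational detail: who makes the solids call, and when. The team can supply this by making the call from the stored clips at the later measurement already planned, with the surgical details withheld where staffing allows. Absence of masking is a declared feature of a small observational study, and reporting to the attending is not shown to add bias beyond it.

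The possible effect is 0.65 to 0.99 points per assumed point of lost specificity. It would be unimportant near the 35% adult rate. It could matter for a comparison only if the pediatric unplanned rate is low and the lean is several points, and the documents establish neither.

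Sections 6.1 and 16.1 must be reconciled on whether the finding can influence care. That is an editorial repair with no effect on the endpoint, the listed analyses or the sample size, and this review takes no position on which statement is right.
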